## 9.5 Analysis of the Primary Effectiveness Endpoint and Objective

The primary effectiveness endpoint is the incidence of aneurysm occlusion without significant parent artery stenosis at 1 year post-procedure without re-intervention in the FAS population. The primary performance objective is to determine if the incidence is above a pre-specified threshold of 50% with 97.5% confidence.

Previously, in the PUFs IDE study, the same effectiveness endpoint of complete occlusion without major stenosis was evaluated. For subject with small and medium wide-necked IAs, treatment options for sustained occlusion are fairly limited. Currently, these IAs are commonly treated with stent-assisted coiling. Published literature on stent-assisted coil embolization has reported an occlusion rate at 1 year post-procedure ranging 46% to 75%. Aneurysm recanalization rates up to 28% have been reported; often requiring the subject to be retreated. Given that these rates represent the effectiveness of the current treatment alternative, a threshold of 50% will be established for the primary effectiveness endpoint.

Primary effectiveness evaluations of occlusion will be assessed by an independent core laboratory. The 1-sided 97.5% confidence interval will be calculated using the exact Clopper-Pearson method. Results will be based on the Full Analysis Set. Subjects who fail to complete the 1-year post-procedure evaluation will be counted as having met the primary performance endpoint.

A tipping point analysis will be performed as a sensitivity analysis for the primary effectiveness endpoint. An additional worst-case sensitivity analysis will be prepared, assuming subjects who withdraw prior to

the 1-year evaluation visit experienced significant stenosis, therefore not meeting the primary effectiveness endpoint.

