**Table 8. Observed Incidence at 1 Year Post-Procedure of Aneurysm Occlusion Without Significant Parent Artery Stenosis**

Observed Incidence at 1 Year	Minimum Sample Size
61%	100
62%	83
63%	71
64%	61
65%	53

The maximum number of subjects to be enrolled in this clinical investigation will be 141 subjects, based on an incidence at 1 year of major stroke in the territory supplied by the treated artery or neurological death of 9%. Based on the expected incidence of the primary endpoints, a minimum of 80 subjects will be enrolled.

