### 9.3 Analysis Population

The analysis population will be comprised of the results from 141 treated subjects. Results will be presented based on two populations:

*Intention to Treat* (ITT): defined as all enrolled subjects in whom deployment of the Pipeline™ device was attempted. It is possible that the Pipeline™ device may not reach the target site and the **operator** would not attempt to deploy it, in the rare event that happens, that subject will not be considered part of the ITT population.

*Full Analysis Set* (FAS): defined as a subset of ITT including only those in whom the Pipeline™ device was implanted.

*Per protocol* (PP): defined as all enrolled subjects, had the Pipeline™ device implanted, and were followed without any major protocol deviations.

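### The 50% occlusion goal in Section 9.5 is tested only in implanted subjects, so subjects attempted but never implanted leave the denominator and no described analysis restores them

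*Combined protocol and SAP*

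**What the plan says.** Section 9.3 defines the ITT set as "defined as all enrolled subjects in whom deployment of the Pipeline™ device was attempted". It adds that if the device does not reach the target and deployment is not attempted, "that subject will not be considered part of the ITT population". The FAS is then "defined as a subset of ITT including only those in whom the Pipeline™ device was implanted".

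Section 9.5 states the primary effectiveness endpoint "at 1 year post-procedure without re-intervention in the FAS population" and repeats in its methods paragraph: "Results will be based on the Full Analysis Set". The objective is a rate "above a pre-specified threshold of 50% with 97.5% confidence", and "The 1-sided 97.5% confidence interval will be calculated using the exact Clopper-Pearson method".

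Three other provisions bear on the point:

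- Section 9.5 counts subjects who do not complete the 1-year evaluation as successes. Its sensitivity analyses are a tipping-point analysis, with no detail given, and a worst case for subjects who withdraw before the 1-year visit.
- Section 6 follows subjects who underwent the procedure without receiving an implant for 30 days only.
- Section 5.4 allows a subject not treated at the first procedure to be implanted later, with Day 0 reset to that date.

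**The concern.** The study objective is the effectiveness of the device in treating these aneurysms. A subject in whom the device was tried and never implanted cannot have an aneurysm occluded by it, and is a failure of the treatment strategy. Removing subjects who contribute no successes can only raise the proportion. The design is single-arm with a fixed goal, so no control group loses its technical failures in the same way. At stake is whether a claim of more than 50% occlusion describes everyone in whom treatment was attempted, or only those in whom it was technically possible.

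**Working it through.** **Inputs from the documents.** One-sided 97.5% Clopper-Pearson limit and 50% threshold (Section 9.5); N = 141 (Section 9.2, below Table 8: "The maximum number of subjects to be enrolled in this clinical investigation will be 141 subjects"); planning range for occlusion 61% to 65% (Section 9.2).

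**Assumption.** The non-implant rate is taken as 0% to 10% of attempted subjects. The nearest figure, in Section 1.2.3, is 46 of 47 braids placed in PITA. That is 1/47 = 2.1% not placed, but per braid, in a study of 31 subjects.

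**Reproducing the plan's N.** The upper limit is the 0.975 quantile of Beta(x+1, n−x), with x = rate × n allowed to be fractional. The smallest n with an upper limit below 15% at observed rates of 5%, 6%, 7%, 8% and 9% is 52, 63, 80, 104 and 141. This matches every row of Table 7. N = 141 comes from the safety endpoint.

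**Size of the overstatement.** Let k of 141 attempted subjects never be implanted. Then ITT rate = FAS rate × (141 − k)/141, so the gap is FAS rate × k/141.

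- k = 3 (2.1%): 61 × 3/141 = 1.3 points
- k = 7 (5.0%): 61 × 7/141 = 3.0 points
- k = 14 (9.9%): 61 × 14/141 = 6.1 points

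At a 65% FAS rate the gaps are 1.4, 3.2 and 6.5 points.

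**Effect on the test.** The lower limit is the 0.025 quantile of Beta(x, n−x+1). The table takes the smallest passing FAS result and re-expresses it on 141 attempted. The last column is the chance that the FAS test passes when the true ITT rate is 50%, that is P(X ≥ minimum) with X ~ Binomial(141 − k, 0.5 × 141/(141 − k)).

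| k | Smallest passing FAS result | Same successes on ITT | ITT lower limit | Chance FAS test passes |
|---|---|---|---|---|
| 0 | 83/141 (58.9%) | 83/141 | 50.3%, passes | 2.1% |
| 3 | 81/138 (58.7%) | 81/141 (57.4%) | 48.9%, fails | 4.4% |
| 7 | 79/134 (59.0%) | 79/141 (56.0%) | 47.4%, fails | 8.3% |
| 14 | 76/127 (59.8%) | 76/141 (53.9%) | 45.3%, fails | 18.6% |

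With k = 1 the smallest passing result, 83/140, becomes 83/141 and still passes. With k = 2, 82/139 passes (50.3%) and 82/141 fails (49.6%).

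**How many failures reverse a given result.** Take 141 implanted and add failed attempts until the lower limit is 50% or below.

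- 86/141 (61%): 7 failures, giving 86/148, lower limit 49.7%
- 92/141 (65%): 18 failures, giving 92/159, lower limit 49.8%

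**Why the failure rule must be explicit.** Take k = 5 and the smallest passing FAS result, 80/136. If the population is changed to ITT and nothing else, the five non-implanted subjects have no 1-year evaluation, and the rule in 9.5 makes them successes: 85/141 = 60.3%, lower limit 51.7%. Counted as failures they give 80/141 = 56.7%, lower limit 48.1%.

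**The case against.** The FAS is openly declared. As an estimate of occlusion given an implant, the FAS rate is not distorted by this exclusion; the overstatement is relative to a rate among all attempted, which Section 9.5 does not claim to estimate. That stands, so this is a questionable choice of population and not a contradiction in the text.

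A reader might infer that every failed deployment leaves the denominator, or that the FAS requires a successful implant. The documents do not support this. The FAS definition requires only that a device was implanted; the word successfully appears only in the per-protocol definition in Section 21. A subject whose first braid failed and was replaced, whose device was poorly placed, or who was implanted at a later procedure remains in the FAS. Only those attempted and never implanted drop out.

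A reader might also take about 2% from PITA as the expected failure rate. That figure is per braid, and the protocol does not say that any PITA subject went without an implant. The 5% and 10% cases have no anchor in the documents.

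Finally, deployment success is a secondary endpoint with exact intervals (Section 9.8), and Section 9.3 says in general that results are presented by population. Failed implants would therefore probably be visible, and a reader could rebuild an ITT rate. This lessens the harm but does not settle it: the 50% test is tied to the FAS, and the plan does not say how non-implanted subjects would be scored.

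**Conclusion.** The point holds for subjects attempted but never implanted. It should be fixed, but it does not by itself undermine the effectiveness claim. The direction is certain whenever at least one such subject exists and the FAS contains at least one success. The size depends on a non-implant rate that the documents do not give.

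The inflated pass probabilities assume a true ITT rate of exactly 50%, well below the planning range, and should be compared with the exact test's actual 2.1% as well as its nominal 2.5%. Inside the planning range the consequence is smaller. With 3 failures among 141 attempted, the FAS test passes and the ITT test fails about 12% of the time at a true FAS rate of 61% (power 74.1% against 61.7%), and about 5% at 65% (94.8% against 90.0%).

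The stronger conclusion, that the 50% claim is unreliable whatever the result, is not supported: a rate of 65% in 141 implanted subjects would survive up to 17 failed implants.

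**What to change.** Add to Section 9.5 a required analysis of the 50% goal in the ITT set, with the same one-sided 97.5% Clopper-Pearson limit, in which every subject with attempted deployment and no implant is explicitly counted as not meeting the endpoint. State that this rule overrides the 9.5 rule for subjects without a 1-year evaluation. Report the result beside the FAS result. Preferably make it the primary test and keep the FAS as supportive.

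State also that ITT as defined still omits subjects whose device never reached the target and in whom deployment was not attempted, and report their number.

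The cost is protocol and SAP wording. No new data are needed, because the rule fixes the outcome of a never-implanted subject without 1-year imaging. The reported rate becomes slightly less favourable. If the ITT test is made primary, power falls: with 7 failures among 141 attempted, from 72% to 45% at a true FAS rate of 61%, and from 94% to 80% at 65%. The change should be made before outcome data are seen.

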### ***PUFs Study***

The PUFs study was a multicenter, prospective, single-arm trial to evaluate the safety and effectiveness of the Pipeline™ device in complex IAs. One hundred seven subjects with large and giant unruptured wide-necked aneurysms in the petrous to the superior hypophyseal segment of the ICA were treated with the Pipeline™ device. The aneurysms measured  $\geq 10$  mm in diameter and had a neck  $\geq 4$  mm. A total of 104 subjects with 106 aneurysms were included in the primary effectiveness cohort. Of the 106 aneurysms, 78 demonstrated complete occlusion without major stenosis at 180 days (73.6%; 95% posterior probability interval: 64.4%–81.0%). At one year, 87.4% (83/95) of the target aneurysms were completely occluded. There were no cases of aneurysm recurrence. The primary safety endpoint was the occurrence of ipsilateral major stroke or neurologic death at 180 days, which occurred in six of the 107 subjects (5.6%; 95% posterior probability interval: 2.6%–11.7%). At one year follow-up, the rate of ipsilateral major stroke or neurologic death was 5.6%.

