## **9.10 Handling of Missing Data and Deviations**

The number and proportion of subjects eligible will be presented. Subjects who withdraw from the study will be tabulated with the reasons for the withdrawal. For the primary endpoint analyses, the last observed values or conditions will be used for the calculations. Any departure or deviation from these planned statistical methodologies will be documented and discussed in the Statistical Analysis Plan that will include the statistical rationale for divergence.

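### Implanted subjects with no completed 1-year evaluation count as effectiveness successes, so lost follow-up inflates the error rate against the 50% goal

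*Combined protocol and SAP*

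**What the plan says.** Section 9.5 defines primary effectiveness success as occlusion at 1 year, without significant parent artery stenosis and without re-intervention. The aim is to "determine if the incidence is above a pre-specified threshold of 50% with 97.5% confidence". On method and population it says: "The 1-sided 97.5% confidence interval will be calculated using the exact Clopper-Pearson method" and "Results will be based on the Full Analysis Set". Section 9.3 gives the size: "The analysis population will be comprised of the results from 141 treated subjects".

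For missing outcomes, Section 9.5 says: "Subjects who fail to complete the 1-year post-procedure evaluation will be counted as having met the primary performance endpoint". It makes no exception for death, for a missed angiogram, or for a subject who is retreated and then lost.

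Two sensitivity analyses follow. One is a tipping-point analysis. The other is described this way: "An additional worst-case sensitivity analysis will be prepared, assuming subjects who withdraw prior to" the 1-year visit had significant stenosis and therefore failed the endpoint.

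Section 9.10 gives another rule: "For the primary endpoint analyses, the last observed values or conditions will be used for the calculations". The plan does not say which of the two takes precedence.

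**The concern.** A missing-data rule for a test against a fixed goal should not make the goal easier to reach as data are lost, and this one does. With no control arm, nothing cancels the added successes. The lower confidence bound is then computed as if those successes had been observed, so its stated 97.5% confidence no longer holds.

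Three further features make it worse.

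- **Scope.** Read literally, the rule makes an effectiveness success of a subject who dies before 1 year, including a neurological death.
- **Conflict.** Take a subject with residual aneurysm on a 180-day angiogram and no 1-year angiogram. That subject is a failure under Section 9.10 and a success under Section 9.5. With both rules in force, the choice could be made after the data are seen.
- **Intent.** It does not read as a slip for the opposite rule. The next paragraph presents missing-as-failure as an additional worst case, which would be largely redundant if the primary rule already said so.

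At stake is whether a positive primary result can be read as evidence that occlusion exceeds 50%.

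**Working it through.** **Inputs.** Goal 0.50, one-sided 97.5% exact Clopper-Pearson lower bound, Full Analysis Set (Section 9.5); n = 141 (Section 9.3); minimum n = 80 (Section 9.2). No 1-year attrition rate is stated. The 30% in Section 4.1 is screen failure before treatment. I therefore vary the number missing, m.

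**The plan's own figure.** n = 141 comes from Table 7: the smallest n at which an observed 9% has an upper bound below 15%. With beta quantiles and x = 0.09n, the upper bound is 0.1501 at n = 140 and 0.1499 at n = 141. The other Table 7 rows (52, 63, 80, 104) also reproduce.

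**Success threshold.** The lower bound for x successes in n is the 0.025 quantile of Beta(x, n − x + 1).

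- 82/141: 0.4956, fails
- 83/141 (58.9%): 0.5027, passes

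**Effect of the rule.** With m missing subjects counted as successes, only 83 − m of the 141 − m evaluated subjects need to be occluded. If the true rate is 50% and missingness is independent of outcome:

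false-success probability = P(Bin(141 − m, 0.5) ≥ 83 − m)

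| Missing m | Share of 141 | Observed successes needed | False-success probability |
|---|---|---|---|
| 0 | 0% | 83/141 (58.9%) | 2.1% |
| 1 | 0.7% | 82/140 (58.6%) | 2.6% |
| 7 | 5% | 76/134 (56.7%) | 7.1% |
| 14 | 10% | 69/127 (54.3%) | 18.7% |
| 15 | 10.6% | 68/126 (54.0%) | 21.1% |
| 21 | 15% | 62/120 (51.7%) | 39.2% |
| 28 | 20% | 55/113 (48.7%) | 64.7% |

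One missing subject is enough to exceed 2.5%. With 25 missing (17.7%), 58/116, exactly 50%, passes.

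**A device below the goal.** Section 9.5 cites 46% as the bottom of the published 1-year range for stent-assisted coiling. A device with a true rate of 46% would pass with probability P(Bin(127, 0.46) ≥ 69) = 3.7% at 14 missing, and P(Bin(113, 0.46) ≥ 55) = 31.7% at 28 missing.

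**Minimum size.** At n = 80 the threshold is 50 successes. The false-success probability is 9.7% with 8 missing and 35.4% with 16 missing.

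**A rough anchor for attrition.** For the earlier trial of this device, Section 1.2.3 gives a primary effectiveness cohort of 106 aneurysms, and then: "At one year, 87.4% (83/95) of the target aneurysms were completely occluded". The denominator falls by 11/106 = 10.4%. Applied to 141 subjects, that is 0.104 × 141 ≈ 15 missing, the 21.1% row.

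**Power under other rules, 14 missing.** Missing-as-failure: P(Bin(127, p) ≥ 83). Evaluable subjects only, where 76/127 is needed: P(Bin(127, p) ≥ 76). At p = 0.50 these are the type I error rates.

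| True rate p | Missing as failure | Evaluable only |
|---|---|---|
| 0.50 | 0.03% | 1.6% |
| 0.61 | 18% | 64% |
| 0.65 | 51% | 90% |
| 0.70 | 89% | 99% |

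At 73.6%, the earlier trial's 180-day rate, missing-as-failure gives 98%. With complete data, power is 73% at 61% and 95% at 65%.

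**The case against.** **The sensitivity analyses cover it.** The tipping-point analysis could be specified to run through to all missing subjects failing, and together with the worst case it would expose the problem. This softens the point, but neither analysis decides success. The worst case names only subjects who withdraw, not those who stay in the study and miss the angiogram.

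**The size is hypothetical.** This stands in part. The plan gives no attrition rate, and independence of missingness and outcome is an assumption. The earlier trial counted aneurysms, not subjects; they were large or giant; and the text does not say why the denominator fell from 106 to 95. About 10% is only an illustration. The conclusion does not need it, because one missing subject is enough.

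**Section 9.10 may govern.** If so, the error rates above do not apply. But Section 9.5 is the more specific text, and the conflict is itself a defect.

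**Deaths and retreatments.** Neurological deaths also count in the primary safety endpoint, which limits the practical harm, and treating deaths from any cause as failures is a choice of estimand. A retreated subject already fails by definition; only one who is retreated and then lost is unclear.

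**Observed successes are still needed.** True. With none observed, 83 of 141 subjects (59%) would have to be missing. What attrition supplies is the margin.

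**Conclusion.** The concern holds, and the sentence is wrong as written. If Section 9.5 governs, the primary effectiveness test does not keep its one-sided 2.5% error rate once any implanted subject lacks a completed 1-year evaluation. At a true rate of 50%, with missingness independent of outcome and n = 141, the error is 7.1% at 5% missing, 18.7% at 10% and 64.7% at 20%. At about 18% missing or more, an observed rate at or below the goal can be declared a success. The size depends on an attrition rate that the plan does not state; the direction does not. The conflict with Section 9.10 stands at any rate of attrition.

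**What to change.** Replace the sentence in Section 9.5 with one rule, fixed before 1-year outcomes are reviewed:

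- Death before the 1-year evaluation is a failure. So is any target-aneurysm retreatment before then, including in a subject later lost. The second part makes explicit what the endpoint definition already implies.
- Other missing or unreadable 1-year angiograms are multiply imputed from baseline aneurysm features and the 180-day angiogram where one exists. Alternatively, they are counted as failures. The text must name one of the two.
- Keep the tipping-point analysis, and extend the missing-as-failure sensitivity analysis to every missing evaluation.
- Delete the last-observed-value sentence in Section 9.10 for the primary endpoints.

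I would make imputation primary and missing-as-failure the sensitivity analysis. Imputation keeps more power in the planning range of 61% to 65%: the evaluable-subject figures, a rough guide to it, are 64% and 90% at 10% missing, against 18% and 51% for missing-as-failure. Its weakness is that Section 5.7.2 collects the 180-day angiogram only when done as standard care, so the model may rest mostly on baseline features. Missing-as-failure needs no model and keeps the error at or below 2.1% at n = 141.

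The cost is a protocol amendment with IRB/EC approval (Section 13.1), matching text in the separate Statistical Analysis Plan, and modest extra analysis. No study procedure changes.

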### **5.11.3 Lost to Follow-up**

A subject will be considered lost to follow-up if the subject cannot be reached after three (3) attempts to contact the subject for a follow-up visit. The site must document a minimum of three (3) attempts, and the final documented attempt should be made via registered letter.

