## 9.2 Sample Size Calculation

Estimates were prepared separately for the primary safety and performance endpoints and based on generating a 1-sided 97.5% Clopper-Pearson exact binomial confidence interval. The upper bound of the confidence interval for safety and the lower bound for performance will be examined relative to the respective *a priori* thresholds. For the primary safety endpoint, the null and alternative hypotheses are as follows:

Ho: Incidence at 1 year post-procedure of major stroke in the territory supplied by the treated artery or neurological death  $\geq 0.15$

Ha: Incidence at 1 year post-procedure of major stroke in the territory supplied by the treated artery or neurological death  $< 0.15$

Reasonable estimates of the observed rate were considered to range between 5% and 9%; the sample size estimates under these scenarios are presented in **Table 7** below:

**Table 7. Observed Incidence at 1 Year Post-Procedure of Major Stroke in the territory supplied by the treated artery or Neurological Death**

Observed Incidence at 1 Year	Minimum Sample Size
5%	52
6%	63
7%	80
8%	104
9%	141

For the primary effectiveness endpoint, the null and alternative hypotheses are as follows:

Ho: Incidence at 1 year post-procedure of aneurysm occlusion without significant parent artery stenosis  $\leq 0.50$

Ha: Incidence at 1 year post-procedure of aneurysm occlusion without significant parent artery stenosis  $> 0.50$

Reasonable estimates of the observed rate were estimates at 61% to 65%; the sample size estimates under these scenarios are presented in **Table 8** below:

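### The worst-case effectiveness analysis in 9.5 fails only subjects who withdraw, so it does not cover every missing 1-year result and is not a true worst case

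*Combined protocol and SAP*

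**What the plan says.** Section 9.5 sets the primary rule for missing effectiveness outcomes: "Subjects who fail to complete the 1-year post-procedure evaluation will be counted as having met the primary performance endpoint". Two sensitivity analyses follow. One is a tipping-point analysis, with no detail on which subjects it varies. The other is labelled worst-case: "An additional worst-case sensitivity analysis will be prepared, assuming subjects who withdraw prior to" the 1-year visit are taken to have significant stenosis and therefore to fail.

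Section 5.11 describes how participation can end. Subject withdrawal (5.11.1), discontinuation by the investigator (5.11.2) and loss to follow-up (5.11.3) have separate headings, and a lost subject is one who "cannot be reached after three (3) attempts to contact the subject for a follow-up visit". The wording is not consistent, however. Sections 5.11 and 5.11.2 also describe subjects removed by the investigator or sponsor as withdrawn. Section 21 does not define the term.

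Section 9.10 gives a different rule for the primary endpoint analyses: use the last observed value or condition.

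**The concern.** A worst-case analysis should reverse every favourable imputation made by the primary rule. Here the primary rule covers all subjects who do not complete the 1-year evaluation, while the worst-case rule covers those who withdraw. The second group is smaller unless every missing result comes from a withdrawal.

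This matters because the primary rule imputes success. The worst-case analysis is the natural safeguard against that, and a reader who sees it pass will conclude that missing data could not overturn the result. If some missing subjects are still carried as successes inside it, that conclusion does not follow.

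**Working it through.** **Who is covered**

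| Reason for no 1-year result | Counted as a failure by the worst-case sentence? |
|---|---|
| Subject withdraws consent (5.11.1) | Yes |
| Removed by investigator or sponsor (5.11, 5.11.2) | Probably, since these sections call such subjects withdrawn |
| Lost to follow-up (5.11.3) | Only if withdrawal is read broadly |
| Died before 1 year | Not addressed |
| Still in the study, angiogram missing or unreadable | No, on any reading |

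**Inputs**

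- Method (9.5): "The 1-sided 97.5% confidence interval will be calculated using the exact Clopper-Pearson method".
- Goal (9.5): the rate must be "above a pre-specified threshold of 50% with 97.5% confidence".
- N (9.3): "The analysis population will be comprised of the results from 141 treated subjects". I take the Full Analysis Set to be all 141.
- Planning range for the effectiveness rate (9.2): 61% to 65%.
- Missingness at 1 year: not stated. The only attrition figure is the roughly 30% screen failure in 4.1, which precedes treatment. I assume 7, 14, 21 or 28 missing (about 5%, 10%, 15%, 20% of 141).
- Split by reason: not stated. I assume about half of the missing withdrew (4 of 7, 7 of 14, 10 of 21, 14 of 28).

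**Reproducing the plan's own figure.** N = 141 comes from the safety endpoint, "based on an incidence at 1 year of major stroke in the territory supplied by the treated artery or neurological death of 9" per cent. The smallest n whose exact upper limit, the 0.975 quantile of Beta(x+1, n−x) with x = rate × n left unrounded, lies below 15% is 52, 63, 80, 104 and 141 at 5% to 9%. This matches Table 7 in every row. The corresponding lower-limit method gives 88 at 61% for effectiveness, where Table 8 states 100. Table 8 is therefore conservative, and the difference does not affect this point.

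**Pass mark at N = 141.** The lower limit is the 0.025 quantile of Beta(x, 141−x+1).

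- 82/141 = 58.2%: limit 0.496, fail.
- 83/141 = 58.9%: limit 0.503, first pass.

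**Effect of uncovered subjects.** Let s be the observed successes and k the missing subjects whom the worst-case sentence does not cover. If those k keep the 9.5 primary value, the analysis as written passes when s + k ≥ 83, that is s ≥ 83 − k. A true worst case needs s ≥ 83. Every s from 83 − k to 82 passes as written and fails the true version. With k = 7 that is 76 to 82.

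**Worked example.** With 14 missing, 7 withdrew and k = 7. Evaluated subjects: 141 − 14 = 127, of whom 77 (61%) succeed.

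- Primary rule: 77 + 14 = 91/141, limit 0.560, pass.
- Worst case as written: 77 + 7 = 84/141 = 59.6%, limit 0.510, pass.
- All missing failed: 77/141 = 54.6%, limit 0.460, fail.

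**Across the assumed range** (lower limits, as written / all missing failed)

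| Observed success | 7 missing | 14 missing | 21 missing | 28 missing |
|---|---|---|---|---|
| 61% | 0.517 / 0.496, differ | 0.510 / 0.460, differ | 0.510 / 0.432, differ | 0.503 / 0.404, differ |
| 63% | 0.531 / 0.510, both pass | 0.531 / 0.481, differ | 0.531 / 0.453, differ | 0.517 / 0.418, differ |
| 65% | 0.553 / 0.531, both pass | 0.553 / 0.503, both pass | 0.546 / 0.467, differ | 0.531 / 0.432, differ |
| 70% | 0.605 / 0.582, both pass | 0.597 / 0.546, both pass | 0.590 / 0.510, both pass | 0.575 / 0.474, differ |

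**Chance of passing if the true rate among evaluated subjects is 50%.** This is P(Bin(141 − M, 0.5) ≥ 83 − k), with M missing.

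- No missing data: 0.021.
- M = 14, k = 7: 0.016.
- M = 21, k = 10 or 11: 0.011 or 0.018.
- M = 28, k = 14: 0.012.
- M = 14, k = 9: 0.038.
- M = 21, k = 14: 0.060.

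**The case against.** The case against has four parts.

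1. A reader might infer that discontinued subjects are left as successes. The documents do not support that: 5.11 and 5.11.2 call them withdrawn, so they may already be failed. Section 9.10 tabulates withdrawals with reasons and names no other exit, so a broad reading could take in lost subjects too. This stands. It does not reach subjects who remain in the study without an evaluable angiogram.

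2. The worst-case sentence does not say what value the uncovered subjects take. That they stay successes is inferred from the 9.5 primary rule. An unreadable image at an attended visit may not fall under that rule, and 9.10 conflicts with it. Under last observed value, a subject last imaged with an open aneurysm would be a failure. This stands as a limit on the size. The gap in scope remains under either rule, because neither makes every uncovered subject a failure.

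3. A reader might infer that the plan as a whole leaves the missing-data effect unbounded. That goes too far: a tipping-point analysis over all missing subjects would contain the true worst case. Its scope is not stated, so it mitigates the gap but cannot be relied on to close it.

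4. A reader might infer that the worst-case analysis has an inflated error rate. At a half split it does not: the chance of passing at a true 50% is about 1% to 2%, below the nominal 2.5%. It exceeds 2.5% only if most of the missing did not withdraw, and the documents give no split.

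**Conclusion.** The point holds in a limited form: as written, a passing result from this analysis does not show that missing data could not overturn the effectiveness conclusion.

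The size depends on assumptions that the documents cannot settle: how many results are missing, how many of those subjects withdrew, and that the uncovered subjects keep the 9.5 primary value. At a half split, the two versions disagree at 61% observed success from 7 missing, at 63% from 14 and at 65% by 21. At 70% they disagree only at 28. If every missing subject withdrew, the two versions coincide.

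This is a supportive analysis and does not itself decide study success. It should still be corrected, because it is the stated check on a primary rule that imputes success, and because an undefined term would otherwise be interpreted after the results are known.

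**What to change.** In 9.5, define the worst case as failure for every Full Analysis Set subject without a core-laboratory-evaluable 1-year result, whatever the reason: death, withdrawal, discontinuation, loss to follow-up, missed imaging or unreadable imaging. State that the tipping-point analysis runs over the same set of subjects. Reconcile the 9.5 primary rule with the last-observed-value rule in 9.10, so that the starting point for both sensitivity analyses is clear.

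The cost is a sentence or two in 9.5 and a matching edit in 9.10, with no new data. The downside for the sponsor is a less favourable sensitivity result whenever any missing subject did not withdraw.
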